14.5 Outside Monitoring

Data and Safety Monitoring Board: Safety data will be reviewed by a Data and Safety Monitoring Board (DSMB) that will meet quarterly after enrollment begins. Additional meetings may be held on an *ad hoc* basis. The board will be blinded to subjects' actual study assignments, but may break the blind if safety concerns arise from the blinded data.

Medical Monitor: The NIDA medical monitor will be available for making recommendations to the investigator on the severity of any SAEs, the relatedness to the study medication, and for determining if an SAE should be reported to the FDA in a 7- or 15-day expedited report or an

annual report (**Appendix I**). The NIDA medical monitor will also be responsible for tracking and assessing trends in the SAEs reported.

Clinical Monitors: All investigators will allow representatives of the Sponsor to periodically monitor, at mutually convenient times during and after the study, all eCRFs and corresponding source documents for each subject. These monitoring visits provide the Sponsor with the opportunity to evaluate the progress of the study and to inform the Sponsor of potential problems at the study sites. The monitors will assure that submitted data are accurate and in agreement with source documentation; verify that investigational products are properly stored and accounted for, verify that subjects' consent for study participation has been properly obtained and documented, confirm that research subjects entered into the study meet inclusion and exclusion criteria, and assure that all essential documentation required by good clinical practices guidelines are appropriately filed.

Monitors will conduct a site initiation visit prior to the start of the study. At this visit, they will assure that proper study-related documentation exists, assist in training investigators and other site personnel in study procedures and compliance with good clinical practice guidelines and FDA regulations, confirm receipt of study supplies, and assure that acceptable facilities are available to conduct the study.

Routine monitoring visits by the Sponsor's representatives will be scheduled at appropriate intervals but more frequently at the beginning of the study. At these visits, the monitors will verify that study procedures are being conducted according to the protocol guidelines. At the end of the study they will advise on storage of study records and return of unused investigational products. All sites should anticipate visits by NIDA and the FDA.

14.6 Adverse Events Reporting

In accordance with FDA reporting requirements, all AEs occurring during the course of the clinical trial will be collected, documented, and reported by the principal investigator or sub-investigators according to the specific instructions detailed in this section of the protocol and Appendix I. The occurrence of AEs will be assessed at each study visit starting at the time that informed consent is signed through the end of follow-up at Week 16.

An AE is defined as any reaction, side effect, or untoward event that occurs during the course of the clinical trial, whether or not the event is considered investigational product-related or clinically significant. For this study, AEs will include events reported by the subject, as well as clinically significant abnormal findings on physical examination or laboratory evaluation. A new illness, symptom, sign or clinically significant clinical laboratory abnormality or worsening of a pre-existing condition or abnormality is considered an AE. Stable chronic conditions, such as arthritis, which are present prior to clinical trial entry and do not worsen are not considered AEs. All AEs must be recorded on the AE Form. The AE Form is also used to record follow-up information for unresolved events reported on previous visits.

Each week, a study investigator must review the AE Form completed for the previous week for any events that were reported as continuing. All AEs, including clinically significant abnormal findings on laboratory evaluations, regardless of severity, will be followed by study investigators until satisfactory resolution. AEs should be reported up to 4 weeks following completion of, or termination from the intervention phase of the study.

14.7 Serious Adverse Events

Each adverse event or reaction will be classified by the study investigator as serious or nonserious. Based on the seriousness of the adverse event or reaction appropriate reporting procedures will be followed. The International Conference on Harmonization (ICH) Guideline for Industry: Clinical Safety Data Management: Definitions and Standards for Expedited Reporting, ICH-E2A March 1995, as implemented by the U.S. Food and Drug Administration defines serious adverse event (SAE) or reaction as any untoward medical occurrence that at any dose:

- results in death;
- is life-threatening; (NOTE: The term "life-threatening" in the definition of "serious" refers to an event in which the patient was at risk of death at the time of the event; it does not refer to an event which hypothetically might have caused death if it were more severe.)
- requires inpatient hospitalization or prolongation of existing hospitalization;
- results in persistent or significant disability/incapacity; or
- is a congenital anomaly/birth defect.

In addition, important medical events that may not result in death, be life-threatening, or require hospitalization may be considered a serious adverse drug reaction, when based on appropriate medical judgment that may jeopardize the subject and may require medical or surgical intervention to prevent one of the outcomes listed in the above definition. Subjects that become pregnant during study participation will be taken off study drug. However, subjects may continue to receive counseling for substance abuse or be referred for appropriate treatment. Subjects will be asked to sign a release of information form for study personnel to access medical records to obtain information regarding the outcome of the pregnancy.

An unexpected event is one that is not described with respect to nature, severity, or frequency in the current Investigator's Brochure or product package insert.

Reporting of AEs and SAEs is described in **Appendix I.** There can be serious consequences including ultimately, criminal and/or civil penalties for Sponsors who fail to comply with FDA regulations governing the reporting of SAEs to FDA. The study investigators in this study have the responsibility of promptly reporting all SAEs to NIDA in order that the NIDA, as the IND Sponsor, can comply with these regulations.

If a study subject withdraws from the study or if an investigator decides to discontinue the subject from the study because of a SAE, the subject must have appropriate follow-up medical monitoring. If the subject is hospitalized, medical monitoring will consist of not less than daily

evaluation by physical examination, vital signs, laboratory evaluations, and if applicable, ECG monitoring for significant treatment-emergent abnormalities. Monitoring will continue until the problem prompting hospitalization has resolved or stabilized with no further change expected or is discovered to be clearly unrelated to of investigational products or progresses to death.

15 ANALYTICAL PLAN

15.1 Statistical Hypotheses

Primary Outcome: It is hypothesized that bupropion, as compared to placebo, will increase the proportion of subjects who achieve abstinence (confirmed by at least two methamphetamine-negative urines and no methamphetamine-positive urines) during the last two weeks (Weeks 11 and 12) for non-daily users.

Secondary Outcomes: It is hypothesized that bupropion, compared to placebo, will be associated with an increase in the proportion of subjects who achieve abstinence (confirmed by at least two methamphetamine-negative urines and no methamphetamine-positive urines) each week during the last two weeks (Weeks 11 and 12) for subjects using methamphetamine 18 or less days during the 30 days prior to the start of signing consent. Secondly, it is also hypothesized that bupropion, as compared to placebo, will increase the proportion of subjects with 21 consecutive days of abstinence during which time all urine drug screens must be methamphetamine-negative (both with and without self report), increase the proportion of subjects who reduce their methamphetamine use as compared to baseline use, increase the weekly mean proportion of methamphetamine non-use days according to self-report alone, increase the proportion of methamphetamine negative urine samples, and improve treatment retention. It is hypothesized that bupropion will reduce the severity of methamphetamine dependence, craving, and comorbidity as assessed by the ASI-Lite, the BSCS, the CGI-S, the CGI-O, and the AISRS. It is further hypothesized that in the evaluable population (as defined in section 15.3), bupropion will be significantly more effective than placebo in those subjects who are medication-compliant compared to either the placebo group or subjects who were not medication compliant. This applies to the primary outcome and all secondary outcomes. Medication-compliant subjects are defined as individuals testing positive for bupropion and/or its major metabolite in at least 50% of urine samples (in aggregate) obtained during Weeks 1 through 10 and at least 66% of urine samples (in aggregate) obtained during Weeks 11 and 12.

15.2 OUTCOME MEASURES

The primary outcome measure, abstinence at the end of the 12-week investigational product dosing period confirmed by two weeks of methamphetamine negative urine specimens is considered a clinically significant improvement in methamphetamine use in this study population. In addition, the secondary outcome variables are intended to explore various aspects of the response to bupropion and to identify factors that may be associated with a treatment success. The primary outcome has been chosen because it is an objective measure of stopping methamphetamine use. Some of the secondary outcome variables add a measure of clinical relevance to the reduction of use by requiring either sustained abstinence (21 Days) or a predetermined, substantial overall reduction in use days (25% and by 50% of their baseline use).

15.2.1 Primary Outcome Measure

The primary efficacy outcome measure is a binary measurement of treatment success or failure, where a subject who successfully achieves two weeks of abstinence during the last two weeks of the investigational product dosing period (Weeks 11 and 12) is scored as a success. During the investigational product dosing period, each subject is asked to provide three urine samples per week. A successful outcome requires (1) all urine samples in the last two weeks are negative for methamphetamine (< 300 ng/mL quantitative result of negative qualitative result) and (2) a minimum of two urines samples collected and tested per each of the last two weeks during investigational product dosing. A subject who drops out before the last 2 weeks of the treatment period is scored as a failure in the analysis. A subject who stays on study to the beginning of Week 11 but who does not provide at least 2 urine samples per week during Weeks 11 and 12 is scored as a failure.

15.2.2 Secondary Outcomes Measures Effect on methamphetamine and other drug use during Study Weeks 1-12 (except J)

- A. The secondary efficacy outcome measure is also a binary measurement of treatment success or failure, where a subject who successfully achieves two weeks of abstinence during the last two weeks of the investigational product dosing period (Weeks 11 and 12) is scored as a success. The study population for this outcome measure is defined as those subjects with methamphetamine dependence who report using methamphetamine 18 or less days during the 30 days prior to signing consent.
- B. Methamphetamine non-use weeks during study Weeks 1 through 12. Use weeks are defined as each 7-day period staring with the first day of investigational product administration. A non-use week is any week in which all of the urine drug screens for methamphetamine were negative (< 300 ng/mL). Conversely, a use week is any week in which at least one of the urine drug screens for methamphetamine was positive (≥ 300 ng/mL). If no drug screening results are available, the data for that week is considered as missing.

- **C.** Log₁₀ weekly mean quantitative urine methamphetamine level.
- **D.** The proportion of successful subjects with different patterns in the reduction in drug use examined as follows:
 - The proportion of subjects with 21 consecutive days of abstinence, during which time all urine drug screens must be methamphetamine-negative (quantitative analysis <300ng/ml). Study days between methamphetamine negative urine specimens are considered to be methamphetamine-negative days. If more than three calendar days of urine specimens are missing, then this period is not considered to be abstinent.
 - 2. The proportion of subjects with 21 consecutive days of abstinence, during which time all urine drug screens must be methamphetamine-negative (quantitative <300 ng/mL) and there is no self-report of methamphetamine use (SUR). If one to seven calendar

days of urine specimens are missing, self-reported methamphetamine use will be used for evaluation. If no use is reported and there are no missing self-reports during this time, this period will be considered abstinent. If more than seven calendar days of urine specimens are missing or if any self-report is missing, then this period is not considered to be abstinent.

- 3. The proportion of subjects who decrease the overall proportion of negative methamphetamine use days by SUR by 25% or more of their self-reported use in the 14-day baseline period.
- 4. The proportion of subjects who decrease the overall proportion of negative methamphetamine use days by SUR by 50% or more of their self-reported use in the 14-day baseline period.
- 5. The proportion of subjects who decrease the mean of the log10-transformed methamphetamine quantitative urine concentration by 25% or more of their mean methamphetamine log10-transformed quantitative urine concentration in the 14-day baseline period.
- 6. The proportion of subjects who decrease the mean of the log10-transformed methamphetamine quantitative urine concentration to 50% or less of their mean methamphetamine log10-transformed quantitative urine concentration in the 14-day baseline period.
- **E.** Weekly mean proportion of methamphetamine non-use days based on subjects self report of use (SUR).
- **F.** The maximum number of consecutive methamphetamine non-use days by subjects self report of use (SUR).
- G. The overall proportion of methamphetamine negative urines.
- **H.** Weekly mean proportion of non-use days of other drug use, by other drug according to SUR.
- I. Weekly proportion of negative urines results for other drug use, by drug.
- **J.** The maximum number of calendar days of abstinence during Study Weeks 1-12, during which time all urine drug screens must be methamphetamine-negative (quantitative <300 ng/mL). Study days between urine specimens are considered to be methamphetamine-negative days. If more than three calendar days of urine specimens are missing, then this period is not considered to be abstinent.
- **K.** The maximum number of calendar days of abstinence during Study Weeks 1-12, during which time all urine drug screens must be methamphetamine-negative (quantitative <300 ng/mL) and there is no self-report of methamphetamine use. If one to seven consecutive days of urine specimens are missing, evaluate self-reported methamphetamine use. If no

use is reported and there are no missing self-reports during this time, this period will be considered abstinent. If more than seven calendar days of urine specimens are missing or if any self-report is missing, then this period is not considered to be abstinent.

L Methamphetamine non-use weeks during study Weeks 1 through 8.

Reduction in the severity of methamphetamine dependence, craving, and withdrawal

- M. Change in CGI-O scores since baseline
- **N.** Change in CGI-S scores since baseline
- **O.** Change in ASI-Lite scores since baseline
- **P.** Change in BSCS scores since baseline

Severity of Depression

Q. Change in HAM-D scores since baseline

Severity of ADHD Symptoms

- **R.** Change in AISRS Scores since baseline
- **S.** The overall proportion of subjects who show a 30% improvement in the AISRS score from baseline to Week 4, 8, 12 and the last available AISRS.
- **T**. Change in the hyperactive/impulsive score of the AISRS (score of even numbered questions of AISRS) from baseline to Week 4, 8, 12 and the last available AISRS.
- **U.** Change in the inattentive score the AISRS (score of odd numbered questions of AISRS) from baseline to week 4, 8, 12 and the last available score.

HIV Risk Taking Behaviors

V. Change in HRBS scores since baseline

Treatment Retention

W. Time from start of investigational product administration until study completion or early termination

Safety of Bupropion

X. AEs, clinical laboratory data, physical exams, and vital signs.

Prevention of Relapse to Methamphetamine Use After Completion of Treatment

- Y. Proportion of subjects who met the criteria for being abstinent according to the primary outcome measure during Weeks 11 and 12 who continue to be abstinent Weeks 13 through 16 as determined by self-report and confirmation by methamphetamine negative urine sample.
- **Z.** Proportion of subjects who met the criteria for being abstinent according to the primary outcome measure who continue to be abstinent Weeks 13 through 16 as determined by self-report alone.

The proportions will be calculated using the number of subjects who meet the criteria for continued abstinence as described above by the number who were abstinent during weeks 11 and 12 as defined by the primary outcome measure.

Plasma Levels of Bupropion and BDNF

Bupropion is primarily metabolized in human liver by CYP 2B6, an isoform that shows high interindividual variability in expression and catalysis which has been hypothesized to account for the variability in treatment response and toxicity associated with bupropion. Rapid clearance of bupropion via hydroxylation could account for treatment failure, likewise, slow clearance could account for toxicity. Recently, the 6B haplotype of CYP 2B6 has been shown to be a significant predictor of bupropion hydroxylation in human liver microsomal preparations, thus suggesting that individuals with this haplotype may be poorer responders to treatment. At steady state, the mean C_{max} following a 150-mg dose of bupropion every 12 hours is 136 ng/mL. Bupropion plasma levels will be examined for correlation to CYP 2B6 haplotypes and to treatment success.

Elevated plasma BDNF levels are associated with methamphetamine neurotoxicity, and are known to decline during abstinence from methamphetamine. Since bupropion also has an independent effect on BDNF, plasma samples will be tested for bupropion level at the same timepoints as plasma for BDNF is obtained. This will allow the evaluation of whether BDNF is affected differently in subjects receiving bupropion compared to those receiving placebo, and whether this effect influences methamphetamine use or abstinence. In addition, it is also hypothesized that methamphetamine users who have the BDNF 66Val homozygote will be more likely to benefit from bupropion than those who do not.

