9.1 Inclusion Criteria

Participants must:

- 1. Be males and/or females, between 18 and 65 years-of-age, inclusive.
- 2. Have a DSM-IV diagnosis of methamphetamine dependence as determined by MINI.
- 3. Have at least 1 amphetamine or methamphetamine positive urine specimen (> 500 ng/mL) after the start of screening and before randomization, or provide collateral information to verify recent use if a positive urine sample can't be obtained.
- 4. Report using methamphetamine for 29 or less days during the 30 day period prior to signing consent using the Timeline Follow-back method.
- 5. Be willing and able to comply with study procedures.
- 6. Be able to verbalize understanding of consent forms, able to provide written informed consent for both the main study and genetics study, and verbalize willingness to complete study procedures.
- 7. Be seeking treatment for methamphetamine dependence.
- 8. If female, have a negative pregnancy test during screening and on the first day of investigational product administration and agree to use of one of the following methods of birth control:
 - a. prescription oral contraceptive
 - b. contraceptive patch
 - c. barrier (diaphragm or condom) with spermicide
 - d. intrauterine progesterone or non-hormonal contraceptive system
 - e. levonorgestrel implant
 - f. medroxyprogesterone acetate contraceptive injection
 - g. complete abstinence from sexual intercourse and agree to use another method should sexual activity commence
 - h. hormonal vaginal contraceptive ring
 - i. contraceptive sponge
 - j. surgical sterilization
 - k. partner is surgically sterile
 - 1. be post menopausal for one year

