Following randomization, during the investigational product dosing period of the study and at each of the follow-up visits, urine will be collected 3 times per week (generally Monday, Wednesday, and Friday, barring holidays and schedule conflicts) and sent to a central laboratory. The central laboratory will: a) perform qualitative analysis for the 1st sample collected each week for cocaine, methamphetamine/amphetamines, tetrahydrocannabinol, opiates, and benzodiazepines, b) screen all samples for amphetamines/methamphetamine, creatinine, and c) will quantitate amphetamines and methamphetamine for all samples, qualitatively screened positive for methamphetamine/amphetamines.

All specimens collected and screened positive by the central laboratory for methamphetamine/amphetamines will be subjected to methamphetamine quantitative analysis performed at central laboratory. The back-up sample retained at the site will be stored frozen until the NIDA data coordinating center has notified the site that it can be disposed.

Urine Toxicology Screen Using an Onsite Testing Device. During the screening/baseline period, urine will be collected 3 times per week (generally Monday, Wednesday, and Friday, barring holidays and schedule conflicts). After the backup aliquot and the central laboratory testing aliquot have been obtained, the sample will be analyzed using an on-site testing device (tetrahydrocannabinol, methamphetamine, cocaine, amphetamines, barbiturates, opiates and benzodiazepines). Samples positive for amphetamine/methamphetamine (the on-site testing device has a cutoff of greater than or equal to 500 ng/mL) will be considered as positive for methamphetamine for inclusion criteria purposes.

Medical Urinalysis. Urine will be collected and analyzed for color, appearance, specific gravity, pH, blood, protein, glucose, ketones, leukocytes, bilirubin and nitrites. Analysis will be conducted at a local laboratory.

Urine Pregnancy Test. An on-site qualitative urine pregnancy test that evaluates human β -chorionic gonadotropin will be used.

Bupropion and Metabolite (hydroxybupropion) Assays. Urine samples collected during the treatment period for the bupropion group will be assayed by a central lab for bupropion and its

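### Secondary outcomes D5 and D6 take 25% and 50% of a log10 concentration, so the fall they require varies with baseline and far exceeds 25% or 50%

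*Protocol*

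**What the plan says.** Section 15.2.2 introduces item D with "The proportion of successful subjects with different patterns in the reduction in drug use examined as follows". D5 counts subjects who "decrease the mean of the log10-transformed methamphetamine quantitative urine concentration by 25% or more of their mean methamphetamine log10-transformed quantitative urine concentration" over the 14-day baseline. D6 counts those who "decrease the mean of the log10-transformed methamphetamine quantitative urine concentration to 50% or less of their mean methamphetamine log10-transformed quantitative urine concentration" over the same period. Despite the change from a fall by a percentage to a fall to a percentage, the two rules have the same form: the on-study mean log10 must be at most 0.75 (D5) or 0.50 (D6) times the baseline mean log10.

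The neighbouring items D3 and D4 apply 25% and 50% to self-reported use days. Section 15.2 describes that pair of thresholds as a "substantial overall reduction in use days (25% and by 50% of their baseline use".

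For the primary outcome, section 15.2.1 requires that "all urine samples in the last two weeks are negative for methamphetamine (< 300 ng/mL quantitative result of negative qualitative result". Section 13.6.29 says the central laboratory "will quantitate amphetamines and methamphetamine for all samples, qualitatively screened positive for methamphetamine/amphetamines", so a screen-negative sample has no measured concentration. Section 9.1 lets a subject enter without a positive urine: "or provide collateral information to verify recent use if a positive urine sample can't be obtained". Section 15.4.1 assigns item D to a Chi-square or Fisher's exact test.

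**The concern.** Subtracting logarithms gives a proportional change in concentration. Dividing them does not: the result depends on how large the logarithm was to begin with. A subject who falls from 100,000 to 50,000 ng/mL and one who falls from 1,000 to 500 ng/mL have made the same proportional change but obtain different log ratios.

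D5 and D6 are binary and are compared between arms as proportions, so any misclassification goes straight into the comparison. Because they sit beside D3 and D4 with the same percentages, a reader of the results would naturally take them as the urine counterparts of a 25% and a 50% reduction.

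**Working it through.** **Inputs.** The 0.75 and 0.50 multipliers come from D5 and D6 (section 15.2.2), and the 300 ng/mL negative limit from section 15.2.1. The protocol gives no baseline concentration, so the baseline geometric mean B is an assumption, shown from 1,000 to 100,000 ng/mL. There is no figure in the plan to reproduce; the check is algebra on the rule as written.

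**1. Implied cut and fall.** The D5 condition is log10(on-study) ≤ 0.75 × log10(B), so on-study ≤ B^0.75 and the fall is 1 − B^(−0.25). The D6 condition gives on-study ≤ B^0.5 and a fall of 1 − B^(−0.5).

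| B (ng/mL) | D5 cut | D5 fall | D6 cut | D6 fall |
|---|---|---|---|---|
| 1,000 | 178 | 82.2% | 31.6 | 96.8% |
| 10,000 | 1,000 | 90.0% | 100 | 99.0% |
| 100,000 | 5,623 | 94.4% | 316 | 99.7% |

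**2. What a true 25% or 50% fall looks like.** On the log scale these are −log10(0.75) = 0.125 and −log10(0.5) = 0.301, whatever the baseline. At B = 10,000 (log10 = 4) they are 0.125/4 = 3.1% and 0.301/4 = 7.5% of the log value. At B = 1,000 (log10 = 3) they are 4.2% and 10.0%. A subject who halves the concentration meets D5 only if B^0.25 ≤ 2, that is B ≤ 16 ng/mL, and D6 only if B^0.5 ≤ 2, that is B ≤ 4 ng/mL. At any baseline in the table, halving fails both.

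**3. Against the 300 ng/mL limit.** B^0.5 < 300 whenever B < 300² = 90,000. B^0.75 < 300 whenever B < 300^(4/3) ≈ 2,008. Two examples with quantitated samples, needing no substituted value:
- B = 10,000 and every on-study sample at 150 ng/mL: log10(150)/4 = 2.176/4 = 0.544, above 0.50, so D6 is failed (cut 100), although every sample is negative by the quantitative limit.
- B = 1,000 and every on-study sample at 250 ng/mL: 2.398/3 = 0.799, above 0.75, so D5 is failed (cut 178).

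**4. Screen-negative samples.** If each is assigned a value v (assumed), a subject with only such samples fails D5 when B < v^(4/3) and D6 when B < v².

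| v (ng/mL) | Fails D5 if B below | Fails D6 if B below |
|---|---|---|
| 300 | 2,008 | 90,000 |
| 150 | 797 | 22,500 |
| 100 | 464 | 10,000 |
| 10 | 22 | 100 |
| 1 | 1 | 1 |

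**5. Unit.** B = 10,000 ng/mL is 10 µg/mL, with log10 = 1. In that unit the cuts are 10^0.75 = 5.62 and 10^0.5 = 3.16 µg/mL, falls of 43.8% and 68.4% instead of 90.0% and 99.0%. At 1 µg/mL the logarithm is zero and no fall is required.

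**The case against.** The protocol states openly that the percentage is taken of the log10 value, and section 15.2 attaches its 25%/50% language to use days, not concentration. D5 and D6 could therefore be read as deliberately strict responder rules. Strictness is not an error, and for any given baseline a lower on-study concentration always moves the subject towards response. This stands in part: the rule does track reduced concentration within a subject. It does not explain why the required fall should vary with baseline, and the protocol gives no reason for that.

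A reader might infer that D5 and D6 score complete abstinence as failure. The documents do not establish that. Fully abstinent subjects would give mainly screen-negative samples, and the result then depends on the value assigned. At 1 ng/mL an all-negative subject with B of at least 1 ng/mL passes both outcomes; at 10 ng/mL D6 is failed only for B below 100. The examples under step 3 concern samples that screened positive and quantitated below 300 ng/mL, which is negative by the protocol's limit but is not proof of no use. The value for screen-negatives, here and in outcome C, is commonly left to a statistical analysis plan, so its absence is not a fault. Nor does the protocol say that the mean is taken over positive samples only.

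A reader might also infer that the choice of unit will decide who responds. Every urine methamphetamine limit in the protocol is in ng/mL, so that unit will presumably be used. The unit calculation shows only that the scale is arbitrary.

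Finally, section 4.1.2 gives a half-life of 12 ± 3.2 hours. If urine roughly follows that elimination, 0.301 log10 is one half-life, and 0.125 log10 is 0.125/0.301 × 12 ≈ 5 hours. Thresholds that small could reflect time since last use. This is a fair warning about the choice of threshold, but no defence of the log ratio.

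**Conclusion.** D5 and D6 are wrong as written. They fix a responder rule on a ratio of logarithms, which corresponds to no constant reduction in concentration. Over assumed baselines of 1,000 to 100,000 ng/mL, D5 requires falls of 82% to 94% and D6 falls of 96.8% to 99.7%, and halving fails both. The D6 cut is below the protocol's negative limit for every baseline under 90,000 ng/mL, and the D5 cut for every baseline under about 2,008 ng/mL. A subject whose samples are all negative by the quantitative limit can therefore be a non-responder.

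The algebra needs no assumption; the percentages rest on the assumed baselines and on ng/mL as the unit. For screen-negative samples the outcome cannot be settled from the protocol.

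This is a minor-to-moderate correction to two of many secondary outcomes. The primary outcome is unaffected.

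**What to change.** Define D5 and D6 on the difference in mean log10 concentration, baseline minus on-treatment, and state the intended reduction:
- If 25% and 50% lower geometric mean concentrations are meant, the thresholds are 0.125 and 0.301 log10.
- If a stricter response is meant, state a larger fixed difference and its reason. For example, 1.0 and 2.0 log10 reproduce the 90% and 99% falls that the present rule implies at B = 10,000 ng/mL.

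Check the chosen difference d against whatever value v the analysis plan assigns to screen-negatives, because an all-negative subject then responds only if B ≥ v × 10^d. With v = 150 ng/mL (assumed) that is B ≥ 300 for d = 0.301, but B ≥ 15,000 for d = 2.0.

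The edit is wording only and needs no further assays, but it changes the outcome materially. The 0.125 and 0.301 thresholds are much more lenient than the written rule, so more subjects will respond, and they are more sensitive to time since last use. That trade-off should be acknowledged when the threshold is chosen.
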